Vitamin D deficiency is another critical issue associated with CKD, particularly in children. Research shows that a significant percentage of patients undergoing hemodialysis exhibit low vitamin D levels, which can exacerbate anemia by lowering hemoglobin levels. Vitamin D plays a vital role in erythropoiesis, and its deficiency correlates with increased serum hepcidin levels—a hormone that regulates iron metabolism and can hinder iron absorption and release from stores.

Given the interconnectedness of vitamin D levels, hepcidin concentration, and anemia in children with CKD, research is warranted to explore the effects of vitamin D supplementation on serum hepcidin and ferritin levels. There is currently a lack of studies addressing this relationship,

especially in Indonesia. This research aims to fill the gap in knowledge regarding vitamin D's potential benefits for managing anemia and iron homeostasis disorders in pediatric CKD patients.

Objectives of Trial:

1. **Primary Objective**
 - a. To assess the effect of Vitamin D supplementation on hepcidin and ferritin serum level in children with CKD
2. **Secondary Objective**
 - a. To assess vitamin D, hepcidin, and ferritin level in children with CKD and GFR less than 90 ml/min/1,73 m² before vitamin D3 supplementation
 - b. To assess vitamin D, hepcidin, and ferritin level in children with CKD and GFR more than 90 ml/min/1,73 m² before vitamin D3 supplementation
 - c. To assess vitamin D, hepcidin, and ferritin level in children with CKD and GFR less than 90 ml/min/1,73 m² after vitamin D3 supplementation
 - d. To assess vitamin D, hepcidin, and ferritin level in children with CKD and GFR more than 90 ml/min/1,73 m² after vitamin D3 supplementation
 - e. To compare vitamin D, hepcidin, and ferritin level in children with CKD and GFR less than 90 ml/min/1,73 m² before and after vitamin D3 supplementation
 - f. To compare vitamin D, hepcidin, and ferritin level in children with CKD and GFR more than 90 ml/min/1,73 m² before and after vitamin D3 supplementation
 - g. To compare vitamin D, hepcidin, and ferritin level between children with GFR less than 90 ml/min/1,73 m² and children with GFR more than 90 ml/min/1,73 m² before vitamin D3 supplementation
 - h. To compare vitamin D, hepcidin, and ferritin level between children with GFR less than 90 ml/min/1,73 m² and children with GFR more than 90 ml/min/1,73 m² after vitamin D3 supplementation

Hypothesis:

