1. Serum hepcidin level is lower after vitamin D3 supplementation in children with CKD
2. Serum ferritin level is lower after vitamin D3 supplementation in children with CKD
3. Serum hepcidin level is lower in pediatric CKD patients with GFR more than 90 ml/min/1,73 m² compare to GFR less than 90 ml/min/1,73 m²
4. Serum ferritin level is lower in pediatric CKD patients with GFR more than 90 ml/min/1,73 m² compare to GFR less than 90 ml/min/1,73 m²

Study Design:

Interventional study

Study Population:

Number of samples:

43 subjects

Inclusion criteria:

- Patients aged 2 to 18 years diagnosed with chronic kidney diseases at [name] hospital
- Parents have signed their child's consent to participate in the study

Exclusion criteria:

- History of blood transfusion 3 months prior
- Liver dysfunction
- Sepsis
- Routine consumption of Vitamin D
- Routine consumption of iron supplement
- Patients diagnosed with iron deficiency anemia

Product Description:

Vitamin D3 with the dose of 2,000 IU

Outcomes:

The primary outcomes being measured in this study are serum vitamin D levels, serum hepcidin levels and serum ferritin levels. These outcomes will be measured in children with CKD before and after 6 weeks of vitamin D3 supplementation. We plan to compare these levels in two groups of CKD patients - those with glomerular filtration rate (GFR) <90 mL/min/1.73 m² and those with GFR ≥ 90 mL/min/1.73 m². Measurement will be done by collecting 3 ml of blood to measure the level of vitamin D, hepcidin and serum ferritin.

Statistical analysis will utilize unpaired T test or Mann-Whitney test will be used to compare vitamin D, hepcidin and ferritin serum level in subjects according to the distribution of the data. Paired T Test or McNemar test will also be used to compare proportion of individually matched event for the two groups before and after vitamin D3 supplementation. Lastly, Pearson or Spearman test will be done to assess the correlation between vitamin D level and hepcidin and ferritin serum level.

Conduct of Trial:

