data will be presented as mean values with standard deviation. For inferential statistics, the study will employ Pearson's correlation test to differentiate between groups and assess statistical significance. The significance level is set at $P < 0.05$ for statistical significance and $P < 0.01$ for high significance. The statistical analysis will be conducted using SPSS version 20.0. Important considerations for this study include ensuring an adequate sample size to detect clinically meaningful differences, which will be determined through a sample size calculation. We will account for potential confounding variables, assess whether assumptions are met for the planned statistical tests, handle any missing data appropriately, and conduct sensitivity analyses to evaluate the robustness of results. By addressing these statistical aspects and considerations, our study aims to produce valid and reliable results regarding the effects of vitamin D3 supplementation on serum hepcidin and ferritin levels in children with CKD, comparing outcomes between groups with different glomerular filtration rates ($\text{GFR} < 90 \text{ mL/min/1.73 m}^2$ and $\text{GFR} \geq 90 \text{ mL/min/1.73 m}^2$).

References

Altemose, K. E., Kumar, J., Portale, A. A., Warady, B. A., Furth, S. L., Fadrowski, J. J., & Atkinson, M. A. (2018). Vitamin D insufficiency, hemoglobin, and anemia in children with chronic kidney disease. *Pediatric Nephrology*, 33(11), 2131–2136. <https://doi.org/10.1007/s00467-018-4020-5>

Avner, E. D., Harmon, W. E., Niaudet, P., Yoshikawa, N., Emma, F., & Goldstein, S. L. (Eds.). (2016a). *Pediatric Nephrology*. Springer Berlin Heidelberg. <https://doi.org/10.1007/978-3-662-43596-0>

Avner, E. D., Harmon, W. E., Niaudet, P., Yoshikawa, N., Emma, F., & Goldstein, S. L. (Eds.). (2016b). *Pediatric Nephrology*. Springer Berlin Heidelberg. <https://doi.org/10.1007/978-3-662-43596-0>

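### The statistics section assigns the GFR-group comparison to Pearson's correlation, contradicting the Outcomes section and, on its ordinary reading, not testing a group difference

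*Protocol*

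**What the plan says.** The protocol names its tests in two places.

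- **Outcomes.** After stating "We plan to compare these levels in two groups of CKD patients", defined by GFR below 90 and GFR 90 or above, the section says "unpaired T test or Mann-Whitney test will be used to compare vitamin D, hepcidin and ferritin serum level in subjects according to the distribution", so the choice of test depends on how the measurements are distributed. It then gives a before-after rule: "Paired T Test or McNemar test will also be used to compare proportion of individually matched event for the two groups". Pearson has a separate role: "Pearson or Spearman test will be done to assess the correlation between vitamin D level and hepcidin and ferritin serum level".
- **Statistical Aspects and Considerations.** For inferential statistics, "the study will employ Pearson's correlation test to differentiate between groups and assess statistical significance". No t-test, Mann-Whitney, paired test or Spearman appears there. The section ends by describing the aim as a comparison of outcomes between the two GFR groups.

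The questions these tests must answer are in two other sections. Hypothesis 3 reads "Serum hepcidin level is lower in pediatric CKD patients with GFR more than 90" compared with the lower-GFR group, and hypothesis 4 says the same of ferritin. Secondary objectives g and h begin "To compare vitamin D, hepcidin, and ferritin level between children with GFR less than 90" and the other group, before and after supplementation respectively.

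**The concern.** The two sections give different tests for the same comparison, and neither defers to the other. The sentence in the designated statistics section is also wrong on its ordinary reading. Pearson's coefficient measures linear association between two measured quantities, and that is the role the Outcomes section gives it. Hypotheses 3 and 4 are about a difference in level between two groups of children.

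An analyst who follows the statistics section could report a significant P that reflects a vitamin D–hepcidin association as evidence about GFR groups, or could miss a real group difference. The conflict also widens the room to choose a test after the data are seen.

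**Working it through.** The protocol gives no effect size, SD, power or split between GFR groups, so no planned figure can be reproduced. From the protocol come n = 43 and the 0.05 level. Everything else is assumed: complete data, two-sided tests, a 21/22 split unless stated, and normal markers unless stated. The rates below are simulated.

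**Step 1. The rules side by side**

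| Task | Outcomes | Statistical Aspects and Considerations |
|---|---|---|
| Levels between GFR groups | Unpaired t-test or Mann-Whitney | Pearson's correlation |
| Before versus after | Paired t-test or McNemar | Not named; covered by Pearson only if assessing significance is read broadly |
| Vitamin D with hepcidin or ferritin | Pearson or Spearman | Not mentioned |

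The first row is a direct contradiction. The second is one only on the broad reading.

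**Step 2. Pearson between vitamin D and hepcidin, used as the group test** (40,000 runs)

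With no group difference, the proportion of trials with P<0.05 is:

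| Marker correlation | 0 | -0.2 | -0.3 | -0.4 | -0.5 |
|---|---|---|---|---|---|
| Pearson | 5% | 25% | 51% | 77% | 94% |
| Unpaired t-test | 5% | 5% | 5% | 5% | 5% |

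Fisher's z approximation, Φ(√(n−3)·atanh|ρ| − 1.96) with √40 = 6.325, agrees:
- |ρ| = 0.3: 6.325 × 0.3095 = 1.958, giving about 50%.
- |ρ| = 0.5: 6.325 × 0.5493 = 3.474, giving 93.5%.

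Now shift hepcidin by 1 SD between groups, with equal vitamin D and zero marker correlation. Pearson rejects in 5% of trials and the t-test in 89%. The t-test non-centrality is √(21 × 22 / 43) = 3.28, which gives the same 89% on 41 degrees of freedom.

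**Step 3. Pearson with GFR group coded 0/1**

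Here t = r√(n−2)/√(1−r²) on n−2 = 41 degrees of freedom, which is the pooled t statistic. The P-values were identical at splits 10/33, 15/28 and 21/22. What is lost is the switch to Mann-Whitney. For log-normal markers with a two-fold group ratio (10,000 runs), power is:

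| Split (lower-level group / higher-level group) | SD(log) | Pearson 0/1 = t-test | Mann-Whitney | Difference (points) |
|---|---|---|---|---|
| 21/22 | 0.5 | 98.2% | 99.0% | 0.8 |
| 21/22 | 0.8 | 67.2% | 76.4% | 9.2 |
| 21/22 | 1.0 | 41.4% | 56.8% | 15.4 |
| 10/33 | 1.0 | 15.9% | 44.2% | 28.3 |
| 33/10 | 1.0 | 44.7% | 43.4% | -1.3 |

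**Step 4. Only if the sentence also covers before-after** (40,000 runs)

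| Within-child correlation | 0 | 0.3 | 0.5 | 0.7 |
|---|---|---|---|---|
| Pearson, no change | 5% | 51% | 94% | nearly 100% |
| Pearson, 0.5 SD fall | 5% | 51% | 94% | nearly 100% |
| Paired t-test, no change | 5% | 5% | 5% | 5% |
| Paired t-test, 0.5 SD fall | 62% | 77% | 89% | 98% |

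Pearson does not respond to a change in mean level.

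**The case against.** The strongest defence is that differentiating between groups with Pearson requires a group code, and with a 0/1 code Pearson is the pooled t-test. The arithmetic is right. However, the protocol describes no such coding and uses Pearson elsewhere for two continuous markers. Even on that reading the Mann-Whitney option disappears. How much that costs depends wholly on assumed skewness and split, from nothing to about 28 points, with the largest loss at one extreme split.

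A second defence is that the Outcomes section is the more specific text, and that the statistics section later refers to its planned tests in the plural. A sensible analyst would probably follow Outcomes. Nothing requires it, though, and the conflicting sentence sits in the section meant to govern the analysis. A separate statistical analysis plan would not cure this, because the protocol does not leave the choice open: it makes it twice, incompatibly.

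Three points limit the weight:
- The clear conflict concerns hypotheses 3 and 4 and objectives listed as secondary. The before-after test of the primary objective is affected only on the broad reading. Against this, Outcomes calls all three serum levels primary and plans the GFR comparison for them.
- The rates in Step 2 come from combining the marker correlation in one section with the purpose stated in the other. They show that the method does not fit the question and do not forecast the error in this trial.
- Outcomes already lets the data's distribution decide between t-test and Mann-Whitney, so the conflict adds to an existing freedom and does not create it.

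**Conclusion.** The concern holds. The protocol gives contradictory tests for two of its four hypotheses, and the faulty sentence is the one in Statistical Aspects and Considerations. Followed as a correlation between markers, it does not test the GFR-group difference: its rejection rate is driven by the marker correlation (5% to 94% over correlations from 0 to -0.5 with no group difference), and it finds a 1 SD group difference in 5% of trials where the t-test finds it in 89%. On the most favourable reading, a 0/1 group code, the harm shrinks to losing the Mann-Whitney option. The contradiction itself rests on the text alone. Only its numerical size depends on the assumed split, correlations, effects and distributions. The sentence should be corrected because, followed as written, it can give a wrong answer to a stated hypothesis.

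**What to change.** Delete the Pearson sentence from Statistical Aspects and Considerations and state the same rule there and in Outcomes:

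- **Between GFR groups:** unpaired t-test or Mann-Whitney, as Outcomes already has it.
- **Before versus after, continuous levels:** paired t-test, with Wilcoxon signed-rank as the non-normal alternative. McNemar is for paired binary data and does not fit these levels. This is a separate slip in Outcomes, best corrected in the same edit.
- **Vitamin D with hepcidin or ferritin:** Pearson or Spearman, and for this purpose only.

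The cost is a few sentences of protocol wording, with no new data, visits or patients.

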**EFFECT OF VITAMIN D3 SUPPLEMENTATION ON HEPSIDIN AND FERRITIN SERUM
LEVELS IN CHILDREN WITH CHRONIC KIDNEY DISEASE**

May 1st 2023

EFFECT OF VITAMIN D3 SUPPLEMENTATION ON HEPSIDIN AND FERRITIN SERUM LEVELS IN CHILDREN WITH CHRONIC KIDNEY DISEASE

Protocol

Responsible Personnel

Principal Investigator Contact Information

Name: [name]

Title: MD

Institution: Department of Pediatrics, Faculty of Medicine, Hasanuddin University

Address: [name]

[contact]

Email: [contact]

Summary:

This study aim to assess the effect of Vitamin D administration on Hepcidin and Ferritin serum level in children with chronic kidney diseases. It is a clinical trial involving 43 chronic kidney disease patients at [name] Hospital in Makassar, Indonesia. Subjects are enrolled into two different groups, one with glomerulus filtration rate (GFR) more than 90 mL/min/1,73 m² and the other group consist of children with GFR less than 90 mL/min/1,73 m². Both group will be given the same dose of Vitamin D, which is 2000 IU for 6 weeks. Measurements of vitamin D, hepcidin and ferritin level will be before and after Vitamin D supplementation.

Introduction:

Chronic kidney disease (CKD) is a significant global health issue characterized by a gradual decline in kidney function over time. Defined by the Kidney Disease: Improving Global Outcomes (KDIGO) guidelines, CKD involves abnormalities in kidney structure or function lasting more than three months, which can lead to complications such as anemia. In children, CKD can adversely affect growth patterns and is closely linked to anemia due to reduced erythropoietin production, which disrupts iron homeostasis essential for oxygen transport in the body.

Anemia in CKD patients is primarily driven by iron deficiency, with studies indicating that the incidence ranges from 7.2 to 13.96 per 1,000 people annually, contributing to approximately 800,000 deaths globally. In pediatric populations, the prevalence of anemia among children with CKD is notably high, affecting 36-58% of patients in regions like the United States and Germany. The increasing incidence of CKD in children is likely related to longer life expectancy and improved treatment options, although data on early-stage CKD remain limited.

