This study will be conducted as a clinical trial involving children with chronic kidney disease (CKD). Participants will be divided into two groups based on their glomerular filtration rate (GFR): those with GFR <90 mL/min/1.73 m² and those with GFR ≥ 90 mL/min/1.73 m². All participants will undergo initial blood tests to measure serum levels of vitamin D, hepcidin, and ferritin. Following these baseline measurements, the children will receive vitamin D3 supplementation for a specified period. After the supplementation period, blood tests will be repeated to measure the same parameters. We will then compare the pre- and post-supplementation levels of vitamin D, hepcidin, and ferritin within each GFR group, as well as between the two GFR groups. This approach will allow us to assess the effect of vitamin D3 supplementation on serum hepcidin and ferritin levels in children with CKD, and to determine if the effect differs based on the severity of kidney dysfunction as indicated by GFR.

[figure not shown]

Figure 1. Study Procedure

Statistical Aspects and Considerations:

This study employs a comprehensive statistical approach to analyze the effect of vitamin D3 supplementation on serum hepcidin and ferritin levels in children with chronic kidney disease (CKD). We will utilize both descriptive and inferential statistics to examine their data. Descriptive statistics will be used to summarize the categorical data as counts and ratios, while quantitative

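### The protocol promises to account for confounders but names only unadjusted tests, so the comparison of non-randomised GFR groups is open to confounding and cannot show whether the effect differs by GFR

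*Protocol*

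**What the plan says.** Under Statistical Aspects and Considerations the protocol commits: "We will account for potential confounding variables". It names no confounder and no adjusted model, stratification or matching.

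The tests are named in two places:

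- **Outcomes, between groups:** "unpaired T test or Mann-Whitney test will be used to compare vitamin D, hepcidin and ferritin serum level in subjects".
- **Outcomes, before and after:** "Paired T Test or McNemar test will also be used to compare proportion of individually matched event".
- **Outcomes, correlation:** "Pearson or Spearman test will be done to assess the correlation between vitamin D level and hepcidin and ferritin serum level".
- **Statistical Aspects and Considerations:** "the study will employ Pearson's correlation test to differentiate between groups and assess statistical significance".

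Under Conduct of Trial, children are assigned to a group by their GFR, below 90 or at least 90 mL/min/1.73 m². The Summary adds: "Both group will be given the same dose of Vitamin D". The same Conduct section says the approach will allow the investigators to "determine if the effect differs based on the severity of kidney dysfunction as indicated by GFR". Objectives g and h and hypotheses 3 and 4 also compare marker levels between the GFR groups.

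**The concern.** GFR group is a patient characteristic and both groups get the same supplement, so the between-group comparison is observational. Children from 2 to 18 years are eligible, and nothing balances age across the groups. The promise to deal with confounding is the right response, but no named test can carry it out.

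There is a second, separate difficulty. The aim of finding out whether the effect differs by GFR concerns response to supplementation. The named between-group test compares levels. Two groups that respond identically but start at different levels will still differ at 6 weeks, and a reader could take that difference for a different response.

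At stake is what may be concluded about effect by GFR and, to a lesser degree, how the differences in levels under objectives g and h and hypotheses 3 and 4 are worded. The within-child before-after comparison, which serves the primary objective and hypotheses 1 and 2, is not affected: a fixed characteristic such as sex or GFR group does not confound a child's comparison with itself.

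**Working it through.** **1. Can any named test adjust?** The unpaired t and Mann-Whitney tests take one outcome and one grouping. The paired t and McNemar tests take one outcome at two times. Pearson and Spearman take two variables. That is 0 of 6 with a covariate term. If the Pearson test for differentiating groups means correlating the marker with a group indicator, it is equivalent to the unpaired t test and still unadjusted.

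**2. Does a comparison of 6-week levels answer the effect-by-GFR aim?** Let the groups differ by D0 at baseline and change by m1 and m2 on average. The 6-week difference is D0 + (m2 − m1). If the response is identical, m2 = m1 and the 6-week difference equals D0. The test then picks up the starting difference alone.

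**3. Illustrative size of confounding.** The protocol gives only the total of 43. The group split, imbalance and correlations below are assumptions.

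- Bias in SD units = (group imbalance in the confounder, in SD) × (its correlation with the marker).
- Low: 0.5 × 0.3 = 0.15 SD. High: 1.0 × 0.5 = 0.50 SD.
- Rejection rate of a two-sided 5% unpaired t test with no GFR effect, from the noncentral t distribution:

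| Split | Bias 0.15 SD | Bias 0.50 SD |
|---|---|---|
| 21/22 | 7.7% | 36.0% |
| 28/15 | 7.4% | 33.2% |
| 33/10 | 6.9% | 27.2% |

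A simulation (20,000 runs per scenario, imbalance 0.5 to 0.8 SD, correlation 0.3 to 0.5) agrees. At 22/21 the unadjusted test rejected in 7.7% to 24.6% of runs and at 28/15 in 7.6% to 22.8%. A linear model containing the confounder rejected in 4.7% to 5.3%. With no imbalance, both stayed at about 5%.

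**4. What baseline adjustment gains.** With before-after correlation r, residual variance falls by r²: 25% at r = 0.5 and 49% at r = 0.7. With no baseline difference between the groups, the equivalent sample size is 43/(1 − r²), that is 43/0.75 = 57 and 43/0.51 = 84. If the groups differ at baseline by d SD, group and baseline are correlated and the variance of the group effect is inflated by about 1 + d²/4 for near-equal groups. At d = 1.0 the factor is 1.25, which leaves 43/(0.75 × 1.25) = 46 and 43/(0.51 × 1.25) = 67. The gain shrinks just when adjustment matters most.

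**5. Why the difference in change should stand beside the model.** With equal SDs at both times, the model subtracts r × D0 from the 6-week difference, while a change score subtracts D0. They differ by (1 − r) × D0. For D0 = 0.5 SD that is 0.5 × 0.5 = 0.25 SD at r = 0.5 and 0.3 × 0.5 = 0.15 SD at r = 0.7. In groups that were not randomised, neither is right by default.

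**The case against.** The strongest reply is that covariates and model form are normal content for a statistical analysis plan, which may exist, and that the protocol does not call its list of tests exhaustive. This holds for a missing covariate list, which is not the point here. The protocol itself assigns the unpaired test to comparing levels, and it states an aim that such a test of levels cannot meet.

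Four further replies limit the point.

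- **Restriction.** The exclusions (recent transfusion, liver dysfunction, sepsis, routine vitamin D or iron, iron deficiency anemia) remove some sources of confounding. A reader might infer that the comparison is confounded. The document does not support that, because it gives no imbalance or correlation. It supports only that the comparison is open to confounding, with age the plain example.
- **Plain differences in level.** A reader might infer that the tests for objectives g and h and hypotheses 3 and 4 are invalid. They are not. Those items ask whether levels differ, and an unpaired test answers that. If the groups differ because of age, their levels do differ. The rejection rates above are errors only if the difference is attributed to GFR.
- **Change scores.** The Conduct section can be read as comparing change between groups, which does use baseline. The wording does not settle this, and a change score still leaves age unadjusted.
- **Over-adjustment.** Baseline vitamin D may lie on the path from GFR to the marker; the Introduction links its deficiency both to CKD and to higher hepcidin. Baseline markers may also be consequences of GFR. Adjusting for these could remove part of the difference that hypotheses 3 and 4 ask about. This stands. It is why baseline vitamin D should not be required and why the adjusted model should not replace the comparison of levels.

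**Conclusion.** The point holds in limited form. The commitment on confounders and the named tests do not fit together, and an unpaired test of 6-week levels cannot show whether the effect differs by GFR. Both conclusions follow from the text and need no assumed figure.

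The size cannot be derived from the protocol. The 8% to 36% rejection range rests on an assumed bias of 0.15 to 0.50 SD and a 21/22 split; the 25% to 49% cut in residual variance rests on an assumed r of 0.5 to 0.7, with less gain in precision if the groups differ at baseline. For scale, 43 children give 80% power for a between-group difference of about 0.85 SD (22/21) to 1.01 SD (33/10), so a bias in the assumed range would not be negligible. This should be changed before analysis; it does not undermine the primary before-after objective.

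**What to change.** - **Effect by GFR:** for hepcidin and for ferritin, add one linear model of the log 6-week value on GFR group, log baseline value and age. Report the group effect with a 95% CI, show the unadjusted difference in change beside it, and state that the groups are not randomised.
- **Baseline comparison (objective g):** regress the log baseline marker on GFR group and age.
- **Objectives g and h, hypotheses 3 and 4:** keep the t or Mann-Whitney test as the unadjusted comparison of levels and word the result as association.
- **Covariates:** do not require baseline vitamin D, and keep the set this small for 43 children.
- **Statistical Aspects and Considerations:** replace the general promise with a reference to these models, so that the commitment and the methods agree.

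The cost is wording plus one extra model per outcome in the software already named. Baseline markers are measured in every child and age is known from eligibility, so no new data are needed. The effect-by-GFR model uses two degrees of freedom beyond the group term, leaving 43 − 4 = 39 residual degrees of freedom against 41 for the unpaired t test.
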